6.2 Analysis Sets for Immunogenicity

For the immunogenicity analysis sets described here, participants will be analyzed according to the treatment group they are randomized to, rather than the vaccine the participant received.

6.2.1 Intent-to-Treat Immunogenicity Set

The ITT set consists of all participants who were randomized to the study, regardless of protocol violations, unacceptable visit windows, missed vaccination, or missing data.

The ITT set will be used for supportive analyses at the final analysis only. If the ITT set differs from the overall PP set by more than 10% (ie, the difference between the number of participants in the ITT set and the number of participants in the overall PP set divided by the number of participants in the PP set is greater than 10%), then the primary immunogenicity analyses will also be conducted at the final analysis using the ITT set.

6.2.2 Per-Protocol Sets

The PP sets for analysis of immunogenicity data will be defined for each visit (ie, Visit 1 - Day 1, Visit 5 - Day 29, Visit 9 - Day 57 [Month 2], Visit 14 - Month 7, Visit 20 - Month 13 [EOS] PP sets) and consist of all participants who meet the following criteria:

- Did not have a major protocol deviation
- Received vaccine within the acceptable vaccination window and received full dose[s] of assigned vaccine
- Had immunogenicity samples taken within acceptable visit windows
- Had a pre-vaccination and the corresponding 1 post-vaccination serum sample available for testing. For the Visit 1 – Day 1 PP set, participants will only be required to have a pre-vaccination serum sample available for testing

Protocol mRNA-1893-P101

Participants who miss the second vaccination may still be included in the PP set for Visit 5 immunogenicity data analysis. If the second vaccination occurs outside of the window, the subsequent data may need to be excluded from the PP set for visits occurring after the second vaccination.

In addition, an overall PP set will be defined for modeling across visits. A participant who is included in any one of the per-visit PP sets will be included in the overall PP set.

The PP sets will be used for the primary immunogenicity analyses at each interim analysis and at the final analysis.

7 Statistical Analysis

7.1 General Considerations

Participants will be identified in the listings by the participant identification number concatenated with the site number. For rescreened participants, only the data collected from the last screening will be presented in the data listings and included in the summaries.

Data from participants excluded from an analysis set will be presented in the data listings but not included in the calculation of summary statistics for the corresponding analysis set.

Although date of physical exam is collected in the eCRF, this data will not be presented in the data listings.

The following treatment groups will be used for summary purposes:

- Placebo
- mRNA-1893 10 μg
- mRNA-1893 30 μg
- mRNA-1893 100 μg
- mRNA-1893 250 μg
- mRNA-1893 Total

For categorical variables, frequencies and percentages will be presented. Continuous variables will be summarized using descriptive statistics (number of participants, mean, median, standard deviation [SD], minimum, and maximum). See Appendix B for variable display standards.

When count data are presented, the percentage will be suppressed when the count is zero in order to draw attention to the non-zero counts. A row denoted "Missing" will be included in count tabulations where specified on the shells to account for dropouts and missing values. The denominator for all percentages will be the number of participants in that treatment within the analysis set of interest, unless otherwise specified.

For the change from Baseline safety summaries, Baseline will be defined as the last non-missing measurement (including repeated and unscheduled assessments) before the first vaccination.

For the immunogenicity analyses, Baseline will be defined as the last non-missing assessment collected at Visit Day 1.

Study Day relative to the first vaccination will be calculated as below:

- Study Day prior to the first vaccination will be calculated as: date of assessment/event date of the first vaccination;
- Study Day on or after the date of the first vaccination will be calculated as: date of assessment/event date of the first vaccination + 1;

Study Day relative to the most recent vaccination will be calculated as below:

- Study Day prior to the first vaccination will be calculated as: date of assessment/event date of the first vaccination;
- Study Day on or after the date of the first vaccination but before the second vaccination (if applicable) will be calculated as: date of assessment/event date of the first vaccination + 1;
- Study Day after the date of the second vaccination will be calculated as: date of assessment/event date of the second vaccination + 1; if Study Day is on the same day as the second vaccination, date and time will be compared with the second vaccination date and time. If it is prior to the second vaccination, then study Day is calculated as: date of assessment/event date of the first vaccination + 1; If it is after the second vaccination then Study Day is calculated as: date of assessment/event date of the second vaccination + 1.

For GMT calculation, antibody values reported as below LLOQ will be replaced by $0.5 \times LLOQ$. Values that are greater than the upper limit of quantification (ULOQ) will be converted to the ULOQ. Missing results will not be imputed.

Date Issued: 25May2021

The following timeframes will be defined for reporting safety data in this study:

- Vaccination: First vaccination on Day 1 to 28 days after last vaccination. If a participant receives two vaccinations, this stage starts at the first vaccination on Day 1 and continues through the 28th Day after the 2nd vaccination.
- Within 28 days of vaccination: Consists of all periods that begin with a vaccination and continue through the 28th Day after the vaccination. This is a subset of the vaccination stage. If a participant receives two vaccinations, this stage includes the two 28-Day periods that begin after each vaccination.
- Overall: Begins at the first vaccination on Day 1 and continues through the final safety call.

Analysis sets for the various analyses are defined in Section 6.

The 95% confidence interval (CI) for percentage will be obtained from SAS procedure of Proc Freq using Clopper-Pearson method. The 95% CI for GMT will be calculated based on the t-distribution of the log-transformed values then back transformed to the original scale for presentation.

Expected visit windows for all study assessments are detailed in Appendix A.

All analyses will be conducted using SAS Version 9.4 or higher.

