4.1 Primary Endpoints

The primary endpoints for the study are the following:

- Frequency and grade of each solicited local and systemic reactogenicity adverse reaction (AR) during a 7-day follow-up period after each vaccination
- Frequency and grade of any unsolicited adverse events (AEs) during the 28-day follow-up period after each vaccination
- Frequency of any medically attended adverse event (MAAE), serious adverse event (SAE), and adverse event of special interest (AESI) from Day 1 to the end of study (EOS) Visit at Month 13

Other safety assessments include clinical laboratory test results (hematology, serum chemistry, and coagulation); vital sign measurements; and physical examination findings.

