6.1.2 Safety Set

The Safety Set consists of all participants who received at least 1 dose of study vaccine (mRNA-1893 or placebo).

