7.6 Safety Analysis

Safety assessments will include monitoring and recording of solicited AEs (local and systemic reactogenicity events) and unsolicited AEs, SAEs, AESIs, AEs leading to study withdrawal, MAAEs; clinical laboratory test results (hematology, serum chemistry, and coagulation); vital sign measurements; and physical examination findings. The Toxicity Grading Scale for Healthy Adult and Adolescent Volunteers Enrolled in Preventative Vaccine Clinical Trials [DHHS 2007] will be used to categorize unsolicited AEs, abnormal clinical laboratory test results, and vital sign measurements.

All safety analyses will be based on the Safety set, except that the analyses of solicited AEs will be based on the Solicited Safety sets.

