7.6.2 Adverse Events

An unsolicited AE is any AE reported by the participant that is either (1) not specified as a solicited AE in the protocol or (2) specified as a solicited AR in the protocol, but its onset occurs outside of the protocol-defined post vaccination period for reporting solicited AEs (ie, for the 7 days after each vaccination). A solicited ARs that meet the criteria for an SAE will also be recorded as an unsolicited AE.

A treatment-emergent AE (TEAE) is defined as any AE not present before exposure to vaccine or any AE already present that worsens in intensity or frequency after exposure. Only TEAEs are collected in this study.

An MAAE is defined as an AE that leads to an unscheduled visit to a healthcare practitioner.

Unsolicited AEs will be coded by PT and SOC using MedDRA and summarized by treatment, vaccination (first or second) and overall. Summaries for each vaccination will include AEs that occur during the 28 -day follow-up period after each vaccine.

All summaries of unsolicited AEs will present number and percentage of subjects in each category. For those summaries presented by PT, the preferred terms will be sorted in descending order of frequency within the mRNA-1893 treatment group.

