7.6.2.2 TEAEs by Preferred Term

The following summary tables of TEAEs will be provided by MedDRA PT using frequency counts and percentages (i.e., number and percentage of participants with an event). When summarizing the number and percentage of participants with an event, participants with multiple occurrences of the same AE or a continuing AE will be counted once. Only the maximum severity level will be presented and an AE with missing severity will be counted as Grade 3/severe in the severity summaries. Only the strongest relationship level will be presented and an AE with missing relationship will be counted as related in the relationship summaries.

- All unsolicited TEAEs
- All unsolicited TEAEs by relationship to the study vaccine
- All unsolicited TEAEs by toxicity grade
- All unsolicited TEAEs occurring within 28 days of any vaccination by vaccination
- All unsolicited TEAEs within 28 days of any vaccination by vaccination and toxicity grade

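### Second-vaccination percentages in the by-vaccination unsolicited AE tables are divided by everyone who had at least one dose, not by those who had dose 2

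*SAP*

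**What the plan says.** The denominator follows from three statements in the SAP.

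- SAP 7.1 gives the default: "The denominator for all percentages will be the number of participants in that treatment within the analysis set of interest, unless otherwise specified".
- SAP 7.6 names the analysis set: "All safety analyses will be based on the Safety set". Solicited reactions are the only exception.
- SAP 6.1.2 defines that set: "The Safety Set consists of all participants who received at least 1 dose of study vaccine".

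SAP 7.6.2 then says that unsolicited events are "summarized by treatment, vaccination (first or second) and overall", and adds: "All summaries of unsolicited AEs will present number and percentage of subjects in each category". Two of the five tables listed in SAP 7.6.2.2 are split this way: "All unsolicited TEAEs occurring within 28 days of any vaccination by vaccination" and "All unsolicited TEAEs within 28 days of any vaccination by vaccination and toxicity grade". They display the second of the three primary endpoint components in SAP 4.1: "Frequency and grade of any unsolicited adverse events (AEs) during the 28-day follow-up period after each vaccination".

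The Protocol expects some participants to miss dose 2 and remain in the study (Protocol 3.3.2 and 3.4.7).

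**The concern.** An event can enter the second-vaccination column only if the participant received a second vaccination. Dividing by a group that includes people who never had dose 2 does not give the risk after dose 2. It gives a smaller number, and the gap depends on how many people missed the dose.

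Two features of the plan make this worth correcting. First, SAP section 8 drops the computed difference from pooled placebo and relies on the displayed proportions for comparison, so these percentages are themselves the planned comparison. Second, some of the Protocol's reasons for withholding dose 2 (3.3.2 and 3.4.2.3) are vaccine-related reactions. Missed second doses could therefore differ between dose groups and from placebo, and the columns would then be understated by unequal amounts. The documents give no loss figures, so this is a possibility and not a forecast.

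The plan does take account of dose receipt elsewhere. SAP 6.1.3 defines a separate Solicited Safety Set for each vaccination, and SAP 6.2.2 defines per-visit per-protocol sets and addresses participants who miss dose 2. The by-vaccination unsolicited AE tables have no such provision.

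**Working it through.** **Inputs**

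- N = 24 participants planned per mRNA-1893 dose group (SAP 5.2). Pooled placebo is also 4 × 6 = 24 (SAP Table 1; pooling in Protocol 3.6.6).
- k = number in a group who miss dose 2. The documents give no value; 0 to 4 is assumed.
- n2 = N − k, the number who received dose 2.
- x = participants with an unsolicited event in the 28 days after dose 2.

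**The plan's own figure.** The chance of seeing at least one participant with an event among 24 is 1 − (1 − p)^24. At p = 10% this is 1 − 0.90^24 = 0.920; at p = 5% it is 1 − 0.95^24 = 0.708. Both match the stated 92% and 70.8%. They do not depend on the point at issue.

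**Formula.** The SAP text gives x/N, and the risk among dose-2 recipients is x/n2. Their ratio is (x/N) / (x/n2) = n2/N for any x above zero.

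**Results for x = 6, where the SAP text always gives 6/24 = 25.0%**

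| k missing dose 2 | n2 | n2/N | 6/n2 | Understatement (points) |
|---|---|---|---|---|
| 0 | 24 | 1.000 | 25.0% | 0.0 |
| 1 | 23 | 0.958 | 26.1% | 1.1 |
| 2 | 22 | 0.917 | 27.3% | 2.3 |
| 3 | 21 | 0.875 | 28.6% | 3.6 |
| 4 | 20 | 0.833 | 30.0% | 5.0 |

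**Scale against sampling error.** Clopper-Pearson 95% intervals, the SAP 7.1 method for percentages, are used here only as a yardstick; SAP 7.6.2 asks for no interval on AE percentages.

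| Among dose-2 recipients | As printed |
|---|---|
| 5/23 = 21.7% (7.5% to 43.7%) | 5/24 = 20.8% (7.1% to 42.2%) |
| 4/20 = 20.0% (5.7% to 43.7%) | 4/24 = 16.7% (4.7% to 37.4%) |
| 8/20 = 40.0% (19.1% to 63.9%) | 8/24 = 33.3% (15.6% to 55.3%) |

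In the second row the shift is 3.3 points, against an interval about 38 points wide.

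**Unequal loss.** Take two groups with the same 25% risk after dose 2: one with nobody missing (6/24 = 25.0%) and one with 4 missing (5/20 = 25.0%). The second prints as 5/24 = 20.8%. The denominator alone creates a difference of 25.0 − 20.8 = 4.2 points.

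**What is not affected**

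- The first-vaccination column, because everyone in the Safety Set had a dose.
- The AE overview (SAP 7.6.2.1).
- The 18 tables in SAP 7.6.2.3, which are overall or after any vaccination.
- Solicited reactions.
- Pause-rule rates.
- The primary component covering medically attended, serious and special-interest events.

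**The case against.** The strongest objection is that the default gives way where something else is specified. SAP 7.1 mentions table shells, which are not available here. They may print a dose-2 N, in which case no wrong percentage would ever appear. That limits the finding to the SAP text. It does not remove it, because the text states a rule and nothing in it sets that rule aside for these tables. SAP 7.1 cites the shells for rows of missing values, not for denominators.

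A second objection is that the endpoint wording names no denominator, and the proportion of everyone exposed is a legitimate quantity. True, but it is not the frequency after the second vaccination in those who had one, which is the natural reading of the endpoint. SAP 6.1.3 takes that approach for solicited reactions, although its set also requires some solicited data to have been contributed.

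A third objection is that the consequence is slight, and this largely stands. The loss is assumed, the tables are descriptive, and no decision rule uses the figure. A reader can usually rebuild the rate from the printed count and the disposition table in SAP 7.2. That table uses the ITT set, whereas safety tables follow vaccine received, so the rebuilding is exact only if the two sets agree on who had dose 2.

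**Conclusion.** The point holds as a minor error in the SAP text. As written, second-vaccination percentages in two unsolicited AE tables equal the risk among dose-2 recipients multiplied by n2/N. The factor is exact. Its size rests on an assumed 0 to 4 missed second doses out of 24, which gives 1.000 down to 0.833. If nobody misses dose 2, or if the shells already use recipients, the printed tables are right. Nothing suggests that a dose-selection or safety conclusion would change; the reason to act is that a primary endpoint component should not rest on an unstated denominator.

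**What to change.** Add one sentence to SAP 7.6.2, with a matching definition in SAP 6.1 parallel to 6.1.3: in by-vaccination summaries of unsolicited events, the denominator is the number of Safety Set participants in the treatment group who received that vaccination. Keep the full Safety Set N for overall and any-vaccination tables. If the shells already do this, say so in the SAP text.

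For consistency only, the same denominator could be used in the by-vaccination medication summaries (SAP 7.3), which name the Safety Set explicitly, and in the laboratory and vital-sign shift tables (SAP 7.6.3 and 7.6.4).

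The cost is one sentence or definition and a minor programming change. No new data are needed, because receipt of each vaccination is already tabulated.

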3.6 Statistical Analysis Plans

3.6.1 Primary Endpoints

The following are the primary endpoints of the study:

• Frequency and grade of each solicited local and systemic reactogenicity AE during a 7-day follow-up period after each vaccination

- Frequency and grade of any unsolicited AEs during the 28-day follow-up period after each vaccination
- Frequency of any MAAE, SAE, and AESI from Day 1 to the EOS Visit at Month 13

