7.2 Background Characteristics

Participant Disposition

The number of participants in the following categories will be summarized by treatment group (see Section 7.1) based on the ITT set:

- Safety Set
- Solicited Safety Sets
- **PP Sets**

The number and percentage of participants in each of the following disposition categories will be summarized by treatment group and serostatus, based on the ITT Set:

- Received each study vaccine
- Completed study (A participant who completed 12 months of follow up after the last vaccination received and completed the Month 13 procedures is considered to have completed the study.)

Protocol mRNA-1893-P101

- Prematurely discontinued the study and the reason for discontinuation
- Prematurely discontinued vaccination and the reason for discontinuation

The number of participants that screen fail will be summarized along with the reason for screen failure.

Participant disposition, screen failure, randomization, and analysis set listings will be provided.

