7.6.2.1 Overview of Adverse Events

An overall summary of unsolicited TEAEs including the number and percentage of participants who experience the following will be presented:

- All unsolicited TEAEs
- All unsolicited serious TEAEs
- All unsolicited TEAEs leading to death

- All unsolicited TEAEs leading to vaccination discontinuation
- All unsolicited TEAEs of grade 3 or 4
- All unsolicited TEAEs of special interest
- All unsolicited medically-attended TEAEs

The table will also include number and percentage of participants with unsolicited, treatment-related TEAEs in each of the above categories.

The overall summary will also be summarized separately for flavivirus seropositive and seronegative participants.

In addition, listings containing individual participant data for TEAEs, TEAEs leading to vaccination discontinuation, SAEs, AESIs, and medically-attended TEAEs will be provided separately.

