10.1 Appendix A Analysis Visit Windows for Safety and Immunogenicity Analysis

Table 3 Visit Window Mapping Rules

| Table 3 Visit Window Mapping Rules | | |
|---------------------------------------|--|----------------------------|
| Labs (Hem | atology, Chemistry, and Coagulation) and | l Vital Signs |
| Visit | Target Study Day | Visit Window |
| Day 1 | Date of First Vaccination (1) | Pre-dose |
| Day 1, 1 hour postdose – Vitals only | 1 | ≥ 1 hour post-dose |
| Day 8 - Labs only | 8 | [8,11] |
| Day 29 | Date of Second Vaccination (29) | [29,36] |
| Day 29, 1 hour postdose – Vitals only | 29 | ≥ 1 hour post-dose |
| Day 36 - Labs only | 36 | [36,39] |
| Day 57 (Month 2) – Labs only | 57 | [50,64] |
| | Adverse Events | |
| Stage | Vaccination | Target Time Frame |
| Vaccination | All | [1, 57] |
| Short-Term Follow-up | First | [1,29] |
| | Second | [29,57] |
| Long-Term Follow-up | First | NA |
| | Second | [57, Month 12 Safety Call] |
| Overall | All | [1, Month 12 Safety Call] |

Protocol mRNA-1893-P101

| Immunogenicity | | | | | |
|-------------------------------------|-------------------------------|------------|--|--|--|
| Visit Target Study Day Visit Window | | | | | |
| Day 1 | Date of First Vaccination (1) | Pre-dose | | | |
| Day 29 | 29 | [29,36] | | | |
| Day 57 (Month 2) | 57 | [50,64] | | | |
| Month 7 | 196 | [182,210] | | | |
| Month 13 | 364 | [343, 385] | | | |

Protocol mRNA-1893-P101

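### The SAP's overall and long-term adverse event windows stop at the Month 12 call, although the MAAE/SAE/AESI primary endpoint runs to the Month 13 visit

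*SAP*

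**What the plan says.** **The endpoint runs to Month 13.** Protocol Section 3.6.1 lists as a primary endpoint the "Frequency of any MAAE, SAE, and AESI from Day 1 to the EOS Visit at Month 13". SAP Section 4.1 repeats it, with the period given as "from Day 1 to the end of study (EOS) Visit at Month 13". Collection matches: Protocol Sections 3.5.7.1.3 and 3.5.7.2 and the Schedule of Events (Protocol Table 5) have these events monitored and recorded through Month 13.

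**The reporting windows stop earlier.** SAP Section 7.1 defines the timeframe "Overall: Begins at the first vaccination on Day 1 and continues through the final safety call". In SAP Appendix A, Table 3, the Overall adverse event window is "1, Month 12 Safety Call" and the Long-Term Follow-up window after the second vaccination is "57, Month 12 Safety Call".

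**How the outputs are described.** SAP Section 7.6.2 says unsolicited adverse events are "summarized by treatment, vaccination (first or second) and overall". The overview in Section 7.6.2.1 includes a row for "All unsolicited medically-attended TEAEs" and gives no end date. The SAE and AESI tables in Section 7.6.2.3 cover events after any vaccination, also with no end date.

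**Completion.** In SAP Section 7.2, a participant with 12 months of follow-up after the last vaccination who "completed the Month 13 procedures is considered to have completed the study".

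**The concern.** The SAP gives two different ends for the same safety follow-up. Two programmers could each follow it faithfully and produce different counts for a primary endpoint, one cut at the Month 12 call and one running to the end-of-study visit. The contact that makes a participant a completer would lie outside the period called Overall.

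The Long-Term Follow-up window bears mainly on this endpoint. General unsolicited events are recorded only to Day 57 in the Schedule of Events. After that, its event-recording rows cover only SAEs, MAAEs and AESIs; Protocol Section 3.1 adds events leading to withdrawal.

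MAAEs depend most on how the overview is programmed. Their only dedicated summary is the overview row, with its treatment-related counterpart and serostatus splits, because Sections 7.6.2.2 and 7.6.2.3 contain no MAAE table. SAEs and AESIs also have their own tables.

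Nothing else in the SAP settles the matter. Section 8 lists two changes from the protocol, and a shorter safety period is not one of them. The rule in Section 2 that the SAP prevails over the protocol does not help, because the conflict is inside the SAP.

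**Working it through.** **1. Which contact is the final safety call?** Section 7.1 does not name a month, so count the contacts in Protocol Table 5.

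- Calls: Days 2, 3, 30 and 31 (4), Months 3 to 6 (4), Months 8 to 12 (5). Total 4 + 4 + 5 = 13.
- Clinic visits: Screening, Days 1, 8, 29, 36 and 57, Months 7 and 13. Total 8.

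Both totals match the 13 calls and 8 clinic visits stated in Protocol Section 3.1 and SAP Section 5.1. The thirteenth call is Month 12 and Month 13 is a clinic visit, so Section 7.1 and Appendix A agree with each other and both disagree with Section 4.1.

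**2. Length of the gap.** Inputs:

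- SAP Appendix A (immunogenicity block) targets Month 7 at Day 196 and Month 13 at Day 364. Since 196/7 = 28 and 364/13 = 28, the SAP's months are 28 days long.
- No document gives a day for Month 12. On the same scale it is 12 × 28 = Day 336 (assumption).
- Protocol Table 5 allows ±7 days for the Month 12 call and ±14 days for the Month 13 visit.

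| Case | Gap (days) | Share of follow-up |
|---|---|---|
| Nominal | 364 − 336 = 28 | 28/364 = 7.7% |
| Shortest | (364 − 14) − (336 + 7) = 7 | 7/350 = 2.0% |
| Longest | (364 + 14) − (336 − 7) = 49 | 49/378 = 13.0% |

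**3. Person-time for 120 participants**, assuming full retention:

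- Nominal: 120 × 28/365.25 = 9.2 person-years.
- Shortest: 120 × 7/365.25 = 2.3.
- Longest: 120 × 49/365.25 = 16.1.

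The outer figures would need every participant to sit at the same edge of the windows, so they are bounds.

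**4. Sensitivity to the calendar.** If Month 13 is instead taken as 12 calendar months after a second dose on Day 29, it falls at about Day 29 + 12 × 30.44 = 394.2. The nominal gap is 30.4 days, with a range of 30.4 − 21 = 9.4 to 30.4 + 21 = 51.4. The share is 30.4/394.2 = 7.7%, as before.

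**5. Which events are at risk.** Only those with onset after the Month 12 call. An event first reported at Month 13 but with earlier onset stays inside the window. A participant who already had an event of the same type is already counted. In a dose group of 24, one participant wrongly left out changes the proportion by 1/24 = 4.2 percentage points.

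**The case against.** The mismatch itself is not in dispute; the argument is about its consequence.

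- **The link to the outputs is inferred.** Section 7.6.2 does not cite Section 7.1 when it speaks of overall summaries. The protocol uses nearly the same phrase in Section 3.6.6.2 without defining any such timeframe, so it could simply mean both vaccinations together. This stands as a possible reading. Section 7.1, however, presents its timeframes as those for reporting safety data, and a programmer may reasonably apply them.
- **The tables that carry the endpoint state no end date**, and Section 4.1 is the more specific text. No passage orders late events to be removed, and the SAE, AESI and MAAE listings would still show them. This stands, and it is why loss of events is possible rather than certain.
- **Appendix A heads its adverse event column as a target time frame rather than a visit window**, so its entries may be nominal. That is fair for Appendix A, but it does not change the wording of Section 7.1.
- **The size is uncertain.** With the SAP's Month 13 immunogenicity window (Days 343 to 385) in place of the protocol's ±14 days, the gap would run from 343 − 343 = 0 to 385 − 329 = 56 days. The protocol's visit window is the better basis, because it governs when the visit takes place; the SAP window maps immunogenicity samples. Neither basis says how many events are affected.
- **The stakes are limited.** The analyses are descriptive, the truncation would fall on all arms alike, and SAP Section 8 drops even the computed difference in proportions. This is correct.

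**Conclusion.** The concern holds. SAP Section 7.1 and Appendix A, applied as written, end overall safety reporting at the Month 12 call, while SAP Section 4.1 and Protocol Section 3.6.1 take the MAAE/SAE/AESI endpoint to the Month 13 visit. The shortfall is about a month: nominally 28 days, or 7 to 49 days under the protocol windows, which is 7.7% (2.0% to 13.0%) of follow-up. This rests on the SAP's 28-day months; calendar months give the same nominal share.

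The inconsistency is certain. Its effect on the counts is not, since it depends on how the summaries are programmed and on event rates that the documents do not give. No formal comparison is affected. It should still be corrected, because it leaves the end of a primary safety endpoint open to two readings.

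**What to change.** 1. In SAP Section 7.1, define Overall as first vaccination through the Month 13 end-of-study visit, or last contact if earlier.
2. In Appendix A, Table 3, end the Overall and Long-Term Follow-up adverse event windows at that same visit.
3. In Section 7.6.2.1, add a sentence saying that the overview rows for serious, special-interest and medically attended events use the Overall timeframe.

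The cost is two revised definitions, one added sentence and one end date in programming. No procedure or data collection changes, because these events are already recorded through Month 13.
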